##### **Other Measurement – Performance**

- To evaluate irrigation of the nasal anatomy (as Done/Not Done, which sinus was irrigated)
- To evaluate nasal cavity inflammation and sinuses inflammation using Lund Mackay CT score and Lund Kennedy Endoscopic scoring
- Patient tolerability and Pain assessment will be recorded by a 0-10 scale (when applicable)

### **5 DESCRIPTION OF PATIENT POPULATION**

#### **5.1 Patient Selection**

Patients indicated for balloon sinus dilation procedure by the ENT specialist.

#### **5.2 Subject Enrollment**

- a) Patients who appear to be eligible will be asked if they would like to participate in this study.
- b) Written informed consent will be obtained from each participating patient prior to collecting a patient history or other testing. The patient will be counseled concerning the research nature of this study, and the risks and possible benefits to participation. Participation is fully voluntary.

## 5.3 Inclusion Criteria

1. Male or female patient indicated for balloon sinus dilation procedure by the ENT specialist
2. Patient age: adult (>18 years old)
3. Patients in general good health in the opinion of the investigator as determined by medical history and physical examination
4. A patient who is able to understand the requirements of the study, is willing to comply with its instructions and schedules, and agrees to sign the informed consent

## 5.4 Exclusion Criteria

1. Known history of any significant medical disorder, which in the investigator's judgment contraindicates the patient's participation
2. Patients with known current or previous bleeding disorder receiving anticoagulants (e.g., chronic Coumadin treatment)

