#### **4.3 Study End Points**

##### **Primary - Safety**

All adverse device effects will be captured and summarized as defined in **Section-8**. Adverse device effects (type, frequency, severity) are expected to be similar to those reported in literature for Nasal Endoscopy (section 8).

For this study, the Safety comparison with the data of Nasal Endoscopy reported in literature will be descriptive with no statistical endpoints.

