## 8 RISK ANALYSIS

Risk analysis for The Sinusway device has been conducted as part of FDA 510k submission (K162916). This risk analysis is applicable to the proposed clinical investigation. The potential risks described below will be explained to the subject in the informed consent process.

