### 8.1 Potential risks – (Sinusway):

Endoscopy is a minimally invasive, diagnostic medical procedure. Overall, nasal endoscopy is a safe and low risk procedure. Nonetheless, potential complications such as mucosal trauma and bleeding may occur, particularly in susceptible patients with increased risk of bleeding, such as those receiving aspirin or other anticoagulant medications (i.e. Plavix, Coumadin, etc.). In addition, adverse reactions to the topical decongestants or anesthetic provided prior to the procedure may occur.

Since the Sinusway endoscope will be used in conjunction with balloon sinus dilation, the following risks which are associated with BSD and/or endoscopic sinus surgery are presented.

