### Risk associated with Endoscopic Sinus Surgery

Surgeons performing routine endoscopic interventions are faced with minor complications in 5% and major complications in 0.5–1% [21]

- Infection- A patient with sinusitis is at risk of developing infection (abscesses, meningitis, etc.) Infection risk increases with the invasiveness of the intervention. The rate of intracranial infections where the intervention is maximized is 1.6% and the rate of infection-related mortality is 0.125%. It is comparable to the one of transcranial surgeries not involving the use of an endoscope [5,6,7]. The Risk of Infection following Sinusway use is mitigated since the Sinusway endoscope is a disposable intended for single use only.
- Bleeding- Bleeding may occur, particularly in susceptible patients with increased risk of bleeding, such as those receiving aspirin or other anticoagulant medications (i.e. Plavix, Coumadin, etc.) [20]. The rate of peri- or postoperative bleeding is around 2% altogether; transfusions were required in about 0.2% of cases [8,9].

- Nasomucosal injury- Nasomucosal injury may occur during transnasal endoscopy. Nasomucosal injury was assessed in 1569 patient that underwent unsedated transnasal esophagogastrroduodenoscopy (EGD), at termination of the procedure. Normal mucosa was observed in 68% of cases, redness of mucosa was observed in 19% of cases, oozing hemorrhage was observed in 12% of cases and overt bleeding was observed in 2% of cases. The hemorrhage was self-limiting and no patient required nasopharyngeal treatment [10].

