#### Anticipated adverse events

Anticipated adverse device effects include Infection, Excessive Bleeding, Nasomucosal injury, CSF leakage, Orbital hematoma, Voice changes, Impaired sense of taste or smell, Nasal obstruction, dryness and pain and Adverse reactions to the topical decongestants or anesthetic provided prior to the procedure. Please refer to section 8.1 above

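### Exclusion 2 joins bleeding disorder and anticoagulant treatment into one condition, so neither a chronic Coumadin user without a bleeding disorder nor a patient with a bleeding disorder off anticoagulants is excluded by rule

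*Protocol*

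**What the plan says.** Protocol section 5.4 has two exclusion criteria, and the synopsis repeats them word for word.

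- Exclusion 1 is a judgment clause: "Known history of any significant medical disorder, which in the investigator's judgment contraindicates the patient's participation".
- Exclusion 2 is the only criterion that mentions bleeding or anticoagulants: "Patients with known current or previous bleeding disorder receiving anticoagulants (e.g., chronic Coumadin treatment").

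Section 8.1 describes who is prone to bleeding during nasal endoscopy: "particularly in susceptible patients with increased risk of bleeding, such as those receiving aspirin or other anticoagulant medications (i.e. Plavix, Coumadin, etc".). Its list of endoscopic sinus surgery risks says the same: "Bleeding may occur, particularly in susceptible patients with increased risk of bleeding, such as those receiving aspirin or other anticoagulant medications". Both statements tie the risk to the medication and do not ask for a bleeding disorder as well.

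Section 8.2 makes bleeding a foreseen device effect: "Anticipated adverse device effects include Infection, Excessive Bleeding, Nasomucosal injury". The primary endpoint in section 4.3 is built on such effects: "All adverse device effects will be captured and summarized as defined in" section 8.

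**The concern.** In Exclusion 2 the words about receiving anticoagulants qualify the patients who have a bleeding disorder. A site that applies the sentence literally will enrol a patient on chronic Coumadin who has no bleeding disorder. Yet chronic Coumadin is the example the criterion itself gives, which suggests that anticoagulant treatment was meant to be a reason for exclusion in its own right.

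Two things are at stake. The first is patient safety, because a group that the protocol describes as prone to bleeding is not screened out by any fixed rule. The second is consistent eligibility across the sites of a multi-center study. Under section 6.2 (Visit 2), a patient found on the procedure day not to meet the criteria becomes a screening failure and is left out of the safety analyses. Under section 13, an enrolled patient who was not eligible may be dropped from analysis. Whether the same Coumadin user is counted in the primary endpoint could therefore depend on how a site reads one sentence.

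**Working it through.** The protocol gives no figure to reproduce. The check is one of logic and of cross-reading.

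**Step 1: what the sentence excludes.** Let B be a bleeding disorder, past or present, and A be anticoagulant treatment. As written, the criterion is B and A. With an 'or' it would be B or A.

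| Bleeding disorder (B) | Anticoagulant (A) | Excluded as written | Excluded with 'or' |
|---|---|---|---|
| yes | yes | yes | yes |
| no | yes | no | yes |
| yes | no | no | yes |
| no | no | no | no |

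The sentence excludes 1 of 4 profiles and the 'or' wording excludes 3 of 4. The two middle rows are the gap. Section 8.1 speaks directly to the second row, the anticoagulant user without a disorder. It does not name the third.

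**Step 2: does another provision close the gap?**

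- *Exclusion 1* depends on the investigator's judgment and names no drug. It can reach a bleeding disorder, and it can equally reach the condition for which Coumadin was prescribed. It is a discretionary safeguard for both middle rows.
- *Inclusion 3* (section 5.3) asks for general good health in the investigator's opinion. It is also discretionary.
- *Concomitant medication* is recorded at screening (section 6.2, Visit 1, and Table 1), so Coumadin use will be seen. No rule says what follows from it.
- *PT, PTT and INR* are optional at screening, and no eligibility limit is attached to them.
- *The procedure-day check* (section 6.2, Visit 2) applies the same criteria again, with the same gap.
- *Consent* covers disclosure: "The potential risks described below will be explained to the subject in the informed consent process". Telling a patient about a risk does not screen for it.

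No fixed rule covers either middle row.

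**Step 3: which risk does the study add?** Every candidate is already indicated for balloon dilation (Inclusion 1). By section 6.2 the physician's usual rigid endoscopy comes first, and the dilation may be done with either endoscope. The study adds the Sinusway examinations before and after dilation, and any irrigation that would not otherwise be done. Only that increment depends on the eligibility wording.

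**Step 4: how many patients?** The protocol does not say how common either middle profile is among candidates. The number affected among the up to 15 patients cannot be derived.

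**The case against.** The strongest reply is that the intent is fairly plain. The Coumadin example points to anticoagulant use as a target, so most investigators would supply the missing 'or'. Those who did not could still refuse the patient under Exclusion 1 or Inclusion 3, and section 17 lets the investigator or sponsor withdraw a patient whose health would be compromised. Keeping a Coumadin user out of the study would not spare that patient the dilation. This stands as far as it goes: it narrows the practical gap and limits the risk at issue to the study's own additions. It does not turn discretion into a rule. Exclusion 2 is the criterion that was supposed to be fixed, and that sites would read it differently is a possibility, not an observed fact.

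A reader might infer two stronger points that the protocol does not support.

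- *That section 8.1 contradicts section 5.4.* Section 8.1 calls anticoagulant users susceptible but does not require their exclusion, and section 8 provides for disclosure at consent. A sponsor could coherently choose to admit them.
- *That the wording would visibly distort the bleeding rate.* One might set one bleed in 15 patients (1/15 = 6.7%) against this statement in section 8.1: "The rate of peri- or postoperative bleeding is around 2% altogether". That comparison shows nothing. One event is 6.7% of any 15-patient study, and even at a true rate of 2% the chance of at least one bleed is 1 − 0.98^15 = 26%. The 2% also belongs to endoscopic sinus surgery, whereas section 4.3 names nasal endoscopy as the literature comparator.

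**Conclusion.** The point holds as a badly worded eligibility rule. Read as written, Exclusion 2 leaves two profiles to investigator judgment: the anticoagulant user without a bleeding disorder, whom section 8.1 describes as prone to bleeding, and the patient with a bleeding disorder who takes no anticoagulant. The consequence concerns patient safety and uniform eligibility. It is confined to the added Sinusway examinations and irrigation, and its size in patients cannot be stated. No error rate or power is involved, since the study plans no statistical test and the safety comparison is descriptive.

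The conclusion rests on the literal reading of a sentence that appears identically in two places. That 'or' was intended is an inference from the Coumadin example, and the sponsor has to confirm it. If the sponsor does mean to admit anticoagulated patients, the sentence still needs rewriting to say so.

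**What to change.** In the synopsis and in section 5.4, put a comma and the words 'or patients' between 'disorder' and 'receiving' in Exclusion 2, and leave the rest of the sentence as it is. The sponsor should confirm that 'or' is meant. Because section 8.1 groups aspirin and Plavix with anticoagulant medications, the sponsor should also state whether the criterion covers them.

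The cost is one sentence changed in two places, handled as a protocol amendment. A few candidates may be screened out, and more if aspirin or Plavix users are included. The gain is a fixed bleeding-risk rule that every site applies in the same way.

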## 6 INVESTIGATION PLAN

### 6.1 Study Design

#### Type of Study

This is an open, multi-center, prospective, feasibility study in which the investigational device, the Sinusway, will be tested in a single group of adult patients, male or females.

The rationale behind this feasibility study is to show that access and visualization of the nasal anatomy and paranasal sinuses (Maxillary, Frontal and Sphenoid sinuses) in conjunction with Balloon Sinus Dilation in patients suffering from symptoms attributable to sinusitis is feasible in the office and operating room settings; This is an essential step in the development of a combined dilation and visualization system that will allow visualization, dilation and lavage of the sinuses via their natural ostia during an office visit, and minimize radiation exposure, antibiotic use, multiple office visits, and cost.

This study is proposed after completing a series of clinical cases, which demonstrated that the system is safe and performed well to physician's satisfaction (detailed information on the studies is provided in the Investigator's Brochure).

## Measures to Minimize Bias

No control groups and no randomization will be utilized in this study since its primary objectives are to obtain information on safety, tolerability and usability which may serve as a basis for modification (if required) and future controlled studies.

## 6.2 Study Procedures

### Visits 1: Screening

- Screening will take place within 1 day-30 days before the procedure.
- Patients potentially qualifying for the study will be offered an Informed Consent to sign prior to further evaluation. Any patients not qualifying will be exited from the study as screening failures and will not be included in the safety/effectiveness analyses.
- The following screening assessments will be performed at pre-study for each patient:
  - Medical history (including concomitant medications)
  - Sino-Nasal outcome test (SNOT-20)
  - Vital signs (optional)
  - CT
  - Laboratory blood work within 6 months including Hematocrit, White Blood Cells , PT, PTT, INR, Creatinine and Glucose (optional, only if done prior to surgery)
  - Compliance with inclusion/exclusion criteria
  - Patients found eligible to participate in the study in the initial screening will be scheduled to undergo the Sinusway evaluation.

### Visit 2: Procedure and Study Termination

- **Before the procedure:**
  - Eligible subject/s will attend the Medical Center at the day of procedure and will be inquired by the PI regarding changes to their health status since the screening visit. If at this point it is determined that the patient **does not** meet all Inclusion and Exclusion criteria and cannot be treated, the patient will be exited from the study. These patients will be considered screening failures, and will not be included in any of the safety or efficacy endpoint analyses.
- **Endoscopy:**
  1. Patients may undergo BSD under local anesthesia, intravenous sedation and local anesthesia or under general anesthesia, at physician discretion.
  2. The Sinusway device will be prepared for use per its instructions for use.
  3. Evaluation of the patient with physician's typical rigid endoscope(s). Visualization of the sinuses (frontal, maxillary, sphenoid) will be recorded as performed/failed and an Image of the anatomic landmark will be taken.

4. Following the Evaluation with physician's typical rigid endoscope(s) the evaluation will be repeated using the Sinusway endoscope. Access to the sinuses (frontal, maxillary, sphenoid) will be recorded as performed/failed and an Image of the anatomic landmark will be taken. Nasal Cavity and sinuses inflammation score will be captured using the Lund Mackay CT and endoscopy score.
5. BSD procedure will be performed with either endoscope.
6. Irrigation of the nasal anatomy will be performed and recorded as Done/Not Done and which sinus was irrigated.
7. Following the BSD procedure, repeated evaluation of patient's sinuses and nasal cavity will be performed using the Sinusway endoscope
8. Usability assessment will be completed by physician.
9. If applicable, patient pain assessment using a 0-10 pain Scale and patient tolerability will be captured (Office procedures only)

- **After the procedure:**
  - The patient will recover from the procedure per physician's common practice. Before patient's release, recording of AE, if any, will be performed. Patient will exit the study.

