## 2 SYNOPSIS

Protocol Number	SD-001
Protocol Title	Safety and Effectiveness Evaluation of the Sinusway™ Device for Endoscopy of the Nasal Cavity and Paranasal Sinuses in Conjunction with Sinus Balloon Dilation
Participating Countries	USA
Clinical Phase	Open, multi - center, prospective, feasibility study
Investigational Study Device	Sinusway™, a flexible, steerable endoscope, by 3NT Medical Ltd.
Study Procedures	Up to 15 Patients scheduled for sinus balloon dilation will be examined with Sinusway™ before and as part of balloon sinus dilation in the operation room (OR) or office setting (Office). The patients will attend the following: 1. Visit 1: Screening and Enrollment, as part of pre-operative visit 2. Visit 2: Sinusway evaluation at the time of the procedure
Study Population	15 adult patients, male or female, scheduled for Sinus Balloon Dilation.
Study Purpose	To assess the safety and initial performance of Sinusway™ in patients in terms of access and visualization of the nasal anatomy and paranasal sinuses, usability (alone and in conjunction with balloon dilation instruments), visualization quality, and irrigation.
Study Endpoints	
Primary – Safety Endpoints:
 
 
• Device related adverse events
 
 
Secondary – Performance Endpoints:
 
 
• To evaluate the ability to access and visualize the nasal anatomy including the maxillary, frontal, and sphenoid sinuses.
 
• To evaluate usability by filling a user questionnaire
 
• To evaluate irrigation of the nasal anatomy
 

Inclusion/Exclusion Criteria	
Inclusion Criteria:
 
 
1. Male or female patient indicated for balloon sinus dilation procedure by the ENT specialist
 
2. Patient age: adult (>18 years old)
 
3. Patients in general good health in the opinion of the investigator as determined by medical history and physical examination
 

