## 3.3 The Sinusway Device

Sinusway, developed by 3NT Medical, is a single-use disposable handheld endoscope 2.3mm in diameter that provides a means to visualize the internal cavities of the ear, airways, nose and sinus cavities during diagnostic and therapeutic endoscope procedures.

An ENT specialist may use the device in an operating room (OR) or an office setting, for visualization and for irrigation at anatomic landmarks, including the sinuses cavities, currently inaccessible by existing endoscopes without significant surgical resection of bone and tissue.

3NT endoscopy system (See figure 1 below) includes:

1. A Multi-use handle accessory (re-processible and auto-clavable) – engages the single-use endoscope component and allows the user to mechanically control its articulation through dedicated levers. (see Figure 1, Reusable Handle)
2. A Single-use flexible endoscope (provided sterile) – includes a distal tip CMOS imager and an integrated working channel which allows irrigation through a single channel. It is the only part that comes in contact with the patient and is disposed of at the end of the procedure. (see Figure 2, Disposable Endoscope).
3. A Camera control unit (CCU) – includes a video processor and a white LED light source. The CCU includes an attachment cable which connects to the single-use endoscope, receives video images from the endoscope, and delivers LED light to the endoscope.

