##### **Secondary - Performance**

- To evaluate the ability to access and visualize the nasal anatomy including the maxillary, frontal, and sphenoid sinuses (according to physician discretion). This ability will be verified by observing anatomic landmarks and transillumination (as Done/Not Done/Failed).
- To evaluate usability and user satisfaction- by filling a usability questionnaire regarding the device, including assessment of visualization quality. Will be completed by the user

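### Irrigation is recorded only as Done/Not Done, so a failed Sinusway irrigation cannot be told from one not attempted, and the recording step does not name the instrument

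*Protocol*

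**What the plan says.** The study purpose in the synopsis and the objective in section 4 both name irrigation among the aspects of Sinusway performance to be assessed, and section 4.2 lists an irrigation evaluation. Section 3.3 describes the disposable endoscope as having "an integrated working channel which allows irrigation through a single channel".

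The recording rule appears twice. In section 4.3 it reads "To evaluate irrigation of the nasal anatomy (as Done/Not Done, which sinus was irrigated", and in section 6.2, Visit 2, step 6 it reads "Irrigation of the nasal anatomy will be performed and recorded as Done/Not Done and which sinus was irrigated". Neither place has a failure level or names the instrument.

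Access and visualization are treated differently. Section 4.3 states "This ability will be verified by observing anatomic landmarks and transillumination (as Done/Not Done/Failed", and Visit 2 step 4, which names Sinusway, states "Access to the sinuses (frontal, maxillary, sphenoid) will be recorded as performed/failed".

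The step just before irrigation reads "BSD procedure will be performed with either endoscope". Section 4 also allows additional endoscopes.

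The rank of irrigation differs between sections. In the synopsis, "To evaluate irrigation of the nasal anatomy" stands among the secondary performance endpoints. In section 4.3 it stands under "Other Measurement – Performance".

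**The concern.** A performance measure for a device needs to show when the device was tried and did not work. With two levels, a Not Done entry can mean that irrigation was not needed, was not tried, or was tried and failed. Only the last of these is information about the device. Section 6.1 says the results may inform device modification and later controlled studies, and for that purpose failures are the most useful entries. A failure that is not recorded as such cannot be recovered at analysis, whatever an analysis plan says.

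The second gap is attribution. If the physician irrigated with something other than the Sinusway channel, step 6 as worded would still take the entry Done, under a heading about Sinusway performance.

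**Working it through.** The protocol states no irrigation rate, target or derived sample size, so there is no figure of its own to reproduce. The check is a comparison of the recording rules, followed by an illustration of how much the ambiguity can matter.

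**Comparison of the recording rules**

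| Item | Where | Levels | Failure separate from non-attempt? | Instrument named? |
|---|---|---|---|---|
| Access and visualization | 4.3, Secondary | Done / Not Done / Failed | Yes | Not in that line |
| Access with Sinusway | 6.2, Visit 2, step 4 | performed / failed | Failure recorded; no level for non-attempt | Yes, Sinusway |
| Irrigation | 4.3, Other Measurement | Done / Not Done, plus which sinus | No | No |
| Irrigation | 6.2, Visit 2, step 6 | Done / Not Done, plus which sinus | No | No |

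1. The access line in section 4.3 treats Not Done and Failed as different outcomes, so the protocol itself recognises the distinction. It gives no reason for dropping it for irrigation.
2. Recording which sinus was irrigated gives a list of successes by sinus. It does not say in which other sinuses irrigation was tried, so there is no per-sinus count of attempts.
3. Steps 4 and 7 of Visit 2 name Sinusway and step 6 does not. The visit schedule (Table 1) has no irrigation row that could settle the matter.

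**Illustration of size**

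Inputs: N = 15, the maximum in section 7. The Done counts are assumptions. If D is the number Done and N − D the number Not Done, the same record fits two extremes:
- all Not Done were failures: success = D / N
- all Not Done were not attempted: success = D / D

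With exact (Clopper-Pearson) 95% intervals:

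| Done / Not Done (assumed) | All Not Done failed | All Not Done not attempted |
|---|---|---|
| 14 / 1 | 14/15 = 93.3% (68.1 to 99.8) | 14/14 = 100% (76.8 to 100) |
| 12 / 3 | 12/15 = 80.0% (51.9 to 95.7) | 12/12 = 100% (73.5 to 100) |
| 10 / 5 | 10/15 = 66.7% (38.4 to 88.2) | 10/10 = 100% (69.2 to 100) |
| 8 / 7 | 8/15 = 53.3% (26.6 to 78.7) | 8/8 = 100% (63.1 to 100) |

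The instrument gap can widen the range. Take 12 Done and 3 Not Done. Suppose that 4 of the 12 were irrigated with another instrument and not tried with Sinusway, and that the 3 were Sinusway failures. The device figure is then (12 − 4) / (15 − 4) = 8/11 = 72.7% (39.0 to 94.0), against 80.0% in the table.

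**The case against.** Several points on the other side carry weight.

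- **Instrument.** A reader might infer that the protocol counts irrigation by another instrument as Sinusway performance. It does not say so. The purpose and objective concern Sinusway, section 3.3 places irrigation in its channel, and sections 3.1 and 3.3 say that existing endoscopes cannot ordinarily reach the sinus cavities without surgical opening. The clause allowing either endoscope governs the balloon step only. What stands is narrower: step 6 is silent, so such an entry is possible.
- **Denominator.** A reader might also infer that there is no denominator at all. Step 6 says that irrigation is to be performed, so the treated patients form a patient-level denominator, and on strict adherence a Not Done is either a departure from the protocol or a failure. That is fair, but the record still does not say which of the two occurred, and it gives no per-sinus denominator.
- **No success rate is promised.** Section 7 plans no statistical analysis, and section 4.3 asks only whether irrigation was done and where. This limits the consequence to description. Even so, a descriptive statement about device performance needs to distinguish failure from non-use.
- **The CRF is not shown.** Appendix B might hold fields for failure, reason or instrument. The finding is therefore about the protocol wording; a CRF that followed that wording would have only the two levels.
- **Rank.** Irrigation is secondary only in the synopsis. The section that sets the coding places it lower, which reduces the weight of the point.

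**Conclusion.** The coding defect stands. Irrigation is a stated aspect of Sinusway performance, and the protocol fixes in two places a two-level record that merges failure with non-attempt, although it separates them for access. There is no per-sinus count of attempts, and the instrument is left unstated. The documents do not support the stronger claims that irrigation by another instrument counts as device performance or that no denominator exists.

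The size is modest. No test depends on irrigation, no figure in the protocol is wrong, and the harm is to interpretation. Under the assumed counts the same record is compatible with 93% to 100% when one patient of 15 is Not Done, and with 53% to 100% when seven are. These ranges rest on assumed splits, full enrolment of 15 and one irrigation result per patient. If every patient were irrigated through Sinusway, the ambiguity would not arise. The difference in endpoint rank between the synopsis and section 4.3 is a separate inconsistency and does not make the coding point more serious.

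**What to change.** In section 4.3, Visit 2 step 6 and the CRF:

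1. Record irrigation through the Sinusway channel for each sinus as Done, Not Done (with reason) or Failed.
2. Note whether any other instrument was used to irrigate that sinus.
3. Report, descriptively, Done over Done plus Failed for Sinusway, with non-attempts and their reasons listed separately.
4. Give irrigation the same endpoint rank in the synopsis and in section 4.3.

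The cost is one or two extra CRF fields per sinus and a small text change. No procedure is added. The descriptive rate may turn out less favourable than a plain Done count.
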